3 STUDY OBJECTIVE(S) AND DESIGN

3.1 Study Objective(s)

3.1.1 Primary Objective

 To evaluate the progression free survival (PFS), based on independent radiologic review (IRR), of ASP8273 compared to erlotinib or gefitinib in patients with locally advanced, metastatic or unresectable stage IIIB/IV adenocarcinoma non-small cell lung cancer (NSCLC) with EGFR activating mutations

3.1.2 Secondary Objectives

- Overall survival (OS)
- Overall response rate (ORR) as assessed by IRR
- PFS as assessed by the investigator
- Disease control rate (DCR) as assessed by IRR
- Safety of ASP8273
- To evaluate Quality of Life (QoL) and patient-reported outcome (PRO) parameters as measured by FACT-EGFRI-18, EORTC-QLQ-LC13, EORTC-QLQ-C30 and EQ-5D-5L

3.1.3 Exploratory Objectives

- To evaluate potential biomarkers that may affect treatment outcome
- Evaluation of the pharmacokinetics of ASP8273
- To evaluate the impact of subsequent therapy on progression free survival on next-line therapy (PFS#2)

3.2 Study Design

3.2.1 Study Design

This multinational, open-label randomized study will evaluate ASP8273 compared to erlotinib or gefitinib (1st generation EGFR TKI) as first line therapy in subjects with locally advanced, metastatic or unresectable stage IIIB/IV adenocarcinoma NSCLC (newly diagnosed or recurrent) with EGFR activating mutations (exon 19 deletion or exon 21 L858R), with or without a T790M mutation, who have not previously been treated with an EGFR inhibitor (1st line).

PFS by IRR is the primary variable. Secondary variables include OS, ORR, PFS by the investigator, DCR, safety and QoL/PRO. Exploratory variables include biomarkers, pharmacokinetics and PFS#2 on subsequent therapy.

Approximately 600 subjects will be randomized 1:1 to 1 of 2 treatment arms (Arm A or Arm B). Arm A will receive 300 mg daily of ASP8273 and Arm B will receive either 150 mg erlotinib or 250 mg gefitinib daily, as decided by the investigator prior to randomization. Both arms will follow 28-day cycles of continuous dosing. Subjects will be stratified according to the following: ECOG PS (0, 1 or 2), EGFR mutation status (exon 19

deletion or mutations in exon 21 [L858R]), TKI chosen (erlotinib or gefitinib) and race (Asian versus non-Asian).

Screening will take place up to 28 days prior to subject randomization on cycle 1 day 1. Subjects will start with cycle 1 and continue on to subsequent 28-day cycles until 1 of the discontinuation criteria are met. Subjects will visit the clinic for evaluations on day 1 and day 15 of treatment cycle 1 and then on day 1 of subsequent treatment cycles up to cycle 7. Subjects who continue past cycle 7 will have visits on day 1 of each odd-numbered cycle.

Quality of life will be assessed during each treatment cycle where a visit takes place, at the follow-up visit, and at each of the post-treatment or long-term follow-up survival contacts for 6 months after treatment discontinuation (EQ-5D-5L only).

Imaging will be evaluated at baseline and every 56 days (± 7 days) throughout the study. A blinded independent central reader will review all imaging scans to confirm complete response (CR), partial response (PR), stable disease (SD) or progressive disease (PD) per Response Evaluation Criteria in Solid Tumors (RECIST) V1.1. Disease progression on study drug (PFS#1) should be confirmed by the blinded independent central reader before subjects are discontinued from treatment.

Following discontinuation from study drug, subjects will have a follow-up visit within 30 days after their last dose of drug for safety assessments. If a subject discontinues study drug prior to radiographic disease progression (i.e., PFS#1), the subject should enter the post-treatment follow-up period and continue to undergo imaging assessments every 56 days (+/- 7 days) until PFS#1 is documented or the subject starts another anticancer treatment, whichever occurs earlier.

Following PFS#1, subjects will enter the long-term follow-up period and be followed every 3 months from the date of the follow-up visit for survival status and progression status on subsequent therapy (i.e., PFS#2). All subsequent anticancer therapy including date and site of progression for PFS#2 will be recorded on the case report form. Subjects will be followed until PFS#2 is documented such as investigator-determined progression, death, subject has ended the subsequent anticancer therapy or the subject starts another anticancer treatment, whichever occurs earlier.

Following PFS#2, subjects will enter the survival follow-up period and be followed every 3 months for survival status.

Samples for pharmacokinetics, biomarkers and pharmacogenomics (PGx) as well as formalin fixed paraffin embedded (FFPE) specimens for central analysis will be collected. Eligibility may be determined by a previously documented EGFR mutation result. However, there should be sufficient tissue from the specimen used to generate the EGFR test result to send to the central lab for confirmatory testing. If a subject does not have a previously documented EGFR mutation test result, then a fresh specimen must be obtained and sent to the central lab for eligibility testing. From initial progression (PFS#1), an optional post-progression tumor tissue sample for exploratory biomarker analysis may be collected following centrally confirmed disease progression for subjects who sign a separate informed consent form (ICF).

An independent Data Monitoring Committee (IDMC) will be chartered to oversee safety and the planned futility analysis which will occur after at least 210 PFS events have been observed.

The primary analysis will occur when at least 420 PFS#1 events are observed which is expected to occur approximately 36 months after randomization. Primary endpoint, secondary endpoints and other endpoints will be analyzed at the time of primary analysis.

3.2.2 ASP8273 Dose/Dose Regimen and Administration Period

ASP8273 300 mg and erlotinib 150 mg will be taken orally once daily, on an empty stomach defined as no food for at least 2 hours before and 1 hour after dosing, at approximately the same time(s) every day.

Gefitinib 250 mg will be taken orally once daily, with or without food, at approximately the same time every day.

Concomitant medications should not be administered within 2 hours before or after dosing with ASP8273, erlotinib or gefitinib.

If a study drug dose is missed, it should be taken as soon as the subject remembers unless more than 12 hours has passed since the intended dosing time, in which case the subject should wait and take the next scheduled dose. Subjects should not make up a missed dose by taking a double dose at the next scheduled dose.

3.3 Randomization

Randomization in a 1:1 ratio to each of the 2 treatment arms will be performed via Interactive Response Technology (IRT). Randomization will be stratified by ECOG PS (0, 1 or 2), EGFR mutation type (exon 19 deletion or mutation in exon 21 L858R), TKI chosen (erlotinib versus gefitinib) and race (Asian versus non-Asian). During screening for each subject the site will need to designate in IRT if the subject will receive erlotinib or gefitinib in the event they are randomized to the comparator arm. Prior to the initiation of the study treatment, the site staff will contact the IRT in order to determine the randomly assigned treatment arm. Specific procedures for randomization through the IRT are contained in the study procedures manual.

4 SAMPLE SIZE

Approximately 600 subjects will be randomized in a 1:1 ratio to 2 treatment arms: Arm A (ASP8273) and Arm B (erlotinib or gefitinib). Randomization will be stratified by ECOG PS (0, 1 or 2), EGFR mutation type (exon 19 deletion or mutation in exon 21 [L858R]), TKI chosen (erlotinib versus gefitinib) and race (Asian versus non-Asian). Assuming HR=0.667 (median PFS in Arm A and Arm B are 15.6 months and 10.4 months, respectively), a total of 420 PFS events will provide approximately 95% power to detect a statistically significant difference at type I error rate of 1-sided 0.025.

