- Best overall response rate (CR + PR) by IRR
- PFS by the investigator
- DCR (CR+PR+SD) by IRR
- DOR by IRR
- Safety variables (e.g., adverse events [AEs], laboratory tests, vital sign measurements, electrocardiograms [ECGs])
- QoL and PRO parameters as measured by FACT-EGFRI-18, EORTC-QLQ-LC13, EORTC-QLQ-C30 and EQ-5D-5L

Exploratory

- Plasma T790M and other biomarkers related to EGFR TKI sensitivity and/or resistance
- Plasma pharmacokinetics of ASP8273
- PFS#2 on subsequent therapy

Biomarkers:

Tumor tissue sample (FFPE) will be obtained and sent for central confirmatory testing to evaluate for EGFR activating mutation. The sample sent for confirmatory testing should be from the same specimen as used for local testing for eligibility. A plasma sample will be collected to evaluate EGFR mutations. Plasma and whole blood samples will be collected for exploratory analysis of biomarkers (e.g. EGFR mutation [T790M, C797S], c-Met mutation/amplification, AXL over expression) which are potentially related to EGFR-TKI drug response or resistance. An optional post-progression tumor tissue sample for exploratory analysis of biomarkers (e.g., EGFR mutation [T790M, C797S], c-Met mutation/amplification, and AXL over expression) which are potentially related to EGFR-TKI drug

response or resistance may be collected following locally or centrally confirmed disease progression for subjects who sign a separate ICF.

Statistical Methods:

Sample Size Justification:

Approximately 600 subjects will be randomized in a 1:1 ratio to 2 treatment arms: Arm A (ASP8273) and Arm B (erlotinib or gefitinib, as decided by the investigator).

Randomization will be stratified by:

- ECOG PS: 0,1 or 2
- EGFR mutation status: exon 19 deletion or mutation in exon 21 [L858R]
- TKI chosen (erlotinib or gefitinib)
- Race (Asian vs nonAsian)

Assuming HR=0.667 (median PFS in Arm A and Arm B are 15.6 months and 10.4 months, respectively), 420 PFS events will provide approximately 98.7% power. The type I error is controlled at 1-sided 0.025.

Safety:

The frequency of AEs and the serious AEs will be summarized by system organ class (SOC) and preferred term. In addition, summary statistics will be provided for the following safety parameters:

- Laboratory values
- Vital sign measurements
- ECGs
- ECOG Performance status

Efficacy:

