7.1 Sample Size

Approximately 600 subjects will be randomized in a 1:1 ratio to 2 treatment arms: Arm A (ASP8273) and Arm B (erlotinib or gefitinib). Randomization will be stratified by ECOG PS (0, 1 or 2), EGFR mutation type (exon 19 deletion or mutation in exon 21 [L858R]), TKI chosen (erlotinib versus gefitinib) and race (Asian versus nonAsian). Assuming HR=0.667 (median PFS in Arm A and Arm B are 15.6 months and 10.4 months, respectively), a total of 420 PFS events will provide approximately 98.7% power to detect a statistically significant difference at type I error rate of 1-sided 0.025.

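### SAP Section 4 gives about 95% power for 420 PFS events; its own inputs give about 98.6%, and the protocol states 98.7%

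*SAP*

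**What the plan says.** SAP Section 4 sets out the design in full: "Approximately 600 subjects will be randomized in a 1:1 ratio to 2 treatment arms"; "Assuming HR=0.667 (median PFS in Arm A and Arm B are 15.6 months and 10.4 months, respectively"; and "a total of 420 PFS events will provide approximately 95% power to detect a statistically significant difference", with the test at a "significant difference at type I error rate of 1-sided 0.025".

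Protocol Section 7.1 has the same allocation, hazard ratio, medians, event count and one-sided level, but concludes that "a total of 420 PFS events will provide approximately 98.7% power to detect a statistically significant difference". The protocol synopsis agrees with Section 7.1: "420 PFS events will provide approximately 98.7% power. The type I error is controlled at 1-sided 0.025".

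Three other places bear on the point:

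- The SAP's revision history (Section 8) says that version 2.0 moved Section 4 to 600 subjects and 420 events to bring it into line with protocol version 2.0. It lists no change to the power.
- SAP Section 3.2.1 and protocol Sections 2.2.1 and 7.4.1.1 place the primary analysis at 420 PFS#1 events.
- SAP Section 7.4.1 places it at about 362.

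**The concern.** Two current documents give different power for one test on identical inputs, so at least one figure is wrong. The gap is too wide for rounding: 95% implies a type II error of 5%, while 98.7% implies 1.3%.

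What is at stake is the accuracy of the sample-size statement for the primary endpoint. The SAP describes itself in Section 1 as the more detailed account of the protocol's analysis, and the rationale in protocol Amendment 1 calls this the single pivotal study for registration. The stated operating characteristics ought to be right and to agree. The wrong power also appears in a document that elsewhere carries a second event count, 362, so a reader could be unsure which design the SAP describes.

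**Working it through.** **Inputs** (SAP Section 4, identical in protocol Section 7.1): D = 420 events; hazard ratio 0.667 (medians give 10.4/15.6 = 0.6667); 1:1 allocation; one-sided 0.025, so z = 1.960.

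**Step 1: the stated 95%.** Schoenfeld, 1:1 allocation:

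power = Φ( √(D/4) × |ln HR| − 1.960 )

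- HR from the medians: √105 × ln 1.5 − 1.960 = 10.247 × 0.4055 − 1.960 = 2.195, and Φ(2.195) = 98.59%.
- HR 0.667 as printed: 98.57%.

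Freedman: power = Φ( √D × (1 − HR)/(1 + HR) − 1.960 )

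- HR 0.667: 20.494 × 0.333/1.667 − 1.960 = 2.134, and Φ(2.134) = 98.4%.

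Neither formula gives 95%.

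**Step 2: the protocol's 98.7%.** It lies about 0.1 point above the Schoenfeld result, which is close enough for a figure given as approximate.

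**Step 3: could another standard choice give 95%?**

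| Variant, 420 events | Power |
|---|---|
| Two-sided 0.05 | 98.6% |
| Binding futility stop at 210 events if HR > 1.1 | 98.57% |
| 0.025 read as two-sided, Schoenfeld | 97.2% |
| 0.025 read as two-sided, Freedman | 96.8% |

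The last two contradict the stated one-sided level, and still miss 95%.

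**Step 4: the reverse check.** Events needed for 95% power at HR 0.667:

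- Schoenfeld: 4 × (1.960 + 1.645)² / (ln 0.667)² gives 317.
- Freedman: 326.

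So 420 events is 94 to 103 more than 95% power requires. The hazard ratio at which 420 events do give 95% is exp(−2 × 3.605/√420) = 0.703, which is not the ratio in Section 4.

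**Step 5: the other event count in the SAP.** At 362 events and HR 0.667, Schoenfeld gives 97.1% and Freedman 96.7%. The 95% is therefore not the power of 362 events by these formulas either.

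**Size.** 98.6 − 95 = 3.6 points. The type II error is 1.4% against the 5% implied.

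**The case against.** **The number does no work.** The planning power enters no test, significance level, boundary or analysis set. The futility rule in SAP Section 7.9 is an observed hazard ratio of 1.1 at 210 events and uses no power value. The correct figure is on record twice in the protocol. All of this stands, and it limits the point to a documentation error.

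**Late separation.** The sample size was raised because the PFS curves were expected to separate late (rationale in protocol Amendment 1; SAP Section 7.4.1 also plans for it), so 95% might be an allowance for that. The text does not support this. SAP Section 4 ties its power to a hazard ratio of 0.667 and mentions no delay, and the protocol reports 98.7% on the same assumption. What stands is that 98.6% holds only under a constant hazard ratio. With late separation the power would differ, and the documents give no delay from which to calculate it.

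**Stronger readings that a reader might infer.**

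- *The trial is underpowered.* The error runs the other way: the SAP understates power.
- *A negative primary result would be misread.* That reading would rest on the estimated hazard ratio and its 95% confidence interval, both pre-specified in SAP Section 7.4.1, and not on planning power.
- *The SAP overrides the protocol, so 95% is the operative figure.* Neither document says that the SAP governs.
- *The 95% was certainly carried over.* The protocol's amendment log pairs 362 events with 95% in superseded protocol text, and the SAP's revision history lists no power change. That makes carry-over likely, but SAP version 1.0 is not available to confirm it.

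**Conclusion.** The point holds as a documentation error. SAP Section 4 is wrong on its own inputs: 420 events at a constant hazard ratio of 0.667, with 1:1 allocation and one-sided 0.025, give about 98.6% power (98.4% by Freedman). The protocol's 98.7% is right to within about 0.1 point.

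The conclusion assumes that 420 is the intended event count. SAP Sections 3.2.1 and 4 and the protocol support that, and SAP Section 7.4.1 does not. The conflict between 362 and 420 is a separate matter and the more consequential one, because it bears on when the primary analysis takes place; the power figure does not.

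**What to change.** In SAP Section 4, change the power from 95% to the protocol's 98.7%. Using 98.6% in the SAP alone would be defensible arithmetic but would leave the two documents different. If the sponsor prefers that value, both documents should carry it and name the method.

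In the same revision, reconcile the 362 events in SAP Section 7.4.1 with the 420 in SAP Sections 3.2.1 and 4, and record both changes in the revision history.

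The power correction is a one-figure edit with no effect on the design, the test or the conduct of the trial. SAP Section 1 allows revisions up to database hard lock.

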5 ANALYSIS SETS

In accordance with International Conference on Harmonization (ICH) recommendations in guidelines E3 and E9, the following analysis sets will be used for the analyses.

Detailed criteria for analysis sets will be laid out in Classification Specifications (CS) and the allocation of subjects to analysis sets will be determined prior to database hard lock.

Full Analysis Set (FAS) and Per Protocol Set (PPS) will be used for efficacy analysis. Safety Analysis Set (SAF) will be used for the analyses of safety variables. Pharmacokinetic Analysis Set (PKAS) will be used for pharmacokinetic analyses. The biomarker pharmacodynamics analysis set (PDAS) will be used for all analyses of pharmacodynamics data.

The data from all patients who were enrolled in the study will be included in the data listings. All enrolled subjects are those who signed the informed consent form and were assigned a subject number.

5.1 Full Analysis Set (FAS)

The full analysis set will consist of all subjects who are randomized. This will be the primary analysis set for efficacy analyses.

5.2 Per Protocol Set (PPS)

The per protocol set will consist of the subset of the FAS who do not meet criteria for PPS exclusion. These criteria are to capture relevant non-adherence to the protocol. In addition, subjects in the PPS are required to have both baseline imaging and at least 1 post-baseline imaging scan. The PPS will be a secondary analysis set for efficacy analyses. Select demographic and baseline characteristics may also be summarized for the PPS.

5.2.1 Reasons for Exclusion From PPS

The following reasons may lead to subject's exclusion from PPS:

- Entered into the study even though the subject violates the inclusion or exclusion criteria which may affect the assessment of the efficacy of the study drug
 - o Inclusion criteria that affect efficacy are: #3, #9, #10, #12, #13 and #14.
 - o Exclusion criteria that affect efficacy are: #1, #2, #3, #5, #9, #12, #18, #19 and #21.

For inclusion/exclusion criteria details, refer to Section 3.2 and 3.3 of the study protocol.

- Received study treatment dose/s other than permitted by protocol for more than 14 days
- Administration of anti-NSCLC treatment prohibited by protocol
- No baseline or post-baseline imaging assessment

5.3 Safety Analysis Set (SAF)

For the statistical summary of the safety data, the safety analysis set (SAF) will be used. The SAF consists of all subjects who take at least 1 dose of study medication, and will be used for safety analyses.

5.4 Pharmacokinetics Analysis Set (PKAS)

The pharmacokinetic analysis set (PKAS) consists of the subset of the SAF population for which at least one plasma concentration data is available for whom the time of dosing on the previous day of sampling is known. Additional subjects may be excluded from the PKAS at the discretion of the pharmacokineticist. Any formal definitions for exclusion of subjects or time-points from the PKAS will be documented in the Classification Specifications and determined in the Classification Meeting.

5.5 Pharmacodynamics Analysis Set (PDAS)

The biomarker pharmacodynamics analysis set (PDAS) will include the subjects from the SAF population for whom sufficient pharmacodynamic measurements were collected. The PDAS will be used for all analyses of pharmacodynamics data.

6 ANALYSIS VARIABLES

6.1 Efficacy Endpoints

6.1.1 Primary Efficacy Endpoint

The primary endpoint is PFS assessed by the blinded IRR. For each subject, PFS is defined as the time from the date of randomization until the date of radiological disease progression (i.e., PFS#1) assessed by IRR, or until death due to any cause. If a subject has neither progressed nor died, the subject will be censored at the date of last radiological assessment or at the date of randomization if no post-baseline radiological assessment is available. Subjects who receive any further anticancer therapy for the disease before radiological progression will be censored at the date of the last radiological assessment before the anticancer therapy started. If progression or death occurs after missing 2 scheduled radiological assessments, the subject will be censored at the date of last radiological assessment or at the date of randomization if no post-baseline radiological assessment is available. Missing 2 scheduled imaging assessments is defined as the gap between two imaging assessments is more than 140 days (2.5 times the scheduled imaging assessment interval (2.5 x 56 days)).

PFS (in days) is calculated as:

(Date of death or documented Progression or censoring) – (Date of randomization) +1.

To apply the cut-off date to PFS is to exclude tumor assessments, death and anti-cancer therapy date after cut-off date in the analysis.

Note: Patient cannot be censored at "Not Evaluable (NE)". If NE is the only previous assessment, then PFS will be censored at Day 1.

Sponsor: Astellas Pharma Global Development, Inc.

ISN/Protocol 8273-CL-0302

6.1.2 Secondary Efficacy Endpoints

6.1.2.1 Overall Survival (OS)

OS is defined as the time from the date of randomization until the documented date of death from any cause. All events of death will be included, regardless of whether the event occurred while the subject is still taking study drug or after the subject discontinue study drug. Subjects who are still alive at the time of analysis will be censored at the last day known to be alive or at the analysis cutoff data, whichever is earlier. Subjects died after the analysis cut-off date will be censored at the analysis cut-off date.

OS (in days) is calculated as:

(Date of death or known to be alive) – (Date of randomization) +1.

6.1.2.2 Objective Response Rate (ORR)

Best overall response is determined once all tumor response data for the subject is available. Subjects will be classified by best response on study as outlined in RECIST v1.1 criteria. For best overall response of stable disease (SD), SD must be documented as present at least once after study entry and at least 7 weeks (the minimum required days for first scheduled imaging assessment after first dose) after first dose.

ORR is defined as the proportion of subjects with best overall response as complete response (CR) or partial response (PR) without confirmation based on the RECIST v1.1 as assessed by the blinded IRR. ORR as assessed by the local investigator will be performed as a sensitivity analysis.

Analysis of ORR with confirmation defined as the proportion of subjects with best overall response as confirmed CR or confirmed PR based on the RECIST v1.1 as assessed by the blinded IRR may also be performed. Confirmation of CR or PR should occur at the next scheduled assessment (not less than 4 weeks following the initial assessment at which CR or PR is observed)

